An increasing number of studies supports the view that SCS can restore posture, stepping, and voluntary walking in humans with SCI^{4,7,17}. The prevailing view is that by elevating the functional state of spared spinal sensory-motor networks below the lesion, residual descending pathways can transmit activity that enables and amplifies voluntary motor control¹⁵. Although epidural SCS can enable force production in paralyzed muscles⁷, whether motor improvements are mediated by the corticospinal tract or the reticulospinal remains unknown.

In a 45-min session, we will deliver non-invasive transcutaneous SCS to the lumbosacral enlargement as participants use their SCS-facilitated leg movements to control a non-invasive body-machine interface (BoMI) on a computer screen and perform game-like activities^{62,63}. To determine which kinds of SCS-enabled movements are mediated by corticospinal networks, participants will perform two motor tasks before and after training requiring different degrees of dexterity: precision control vs. maximum range of motion; using two types of movements: hip vs. ankle flexion. To quantify changes in neural excitability of the corticospinal tract, we will compare motor-evoked potentials (MEPs) elicited by transcranial magnetic stimulation of the leg motor cortex⁶⁴ as participants perform the motor tasks. We postulate that MEP responses will be enhanced for the precision-control task in distal muscles (tibialis anterior), which are thought to require a high involvement from the corticospinal tract. *Our hypothesis is that SCS will further enhance the MEP response for these movements, but not for range-of-motion movements, or movements with proximal muscles (rectus femoris).*

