Transcranial magnetic stimulation (TMS): Motor evoked potentials (MEPs) in the tibialis anterior and rectus femoris muscles will be evoked by TMS of the contralateral motor cortical leg area using a Magstim 200² stimulator (Magstim, UK) through a double cone coil and a monophasic current waveform delivered at 4-s intervals. The motor threshold for both muscles will be identified⁶⁵ and that intensity will be used to elicit and average twenty MEPs at each timepoint²⁴. Average MEP response amplitude will be used to quantify changes in corticospinal tract excitability¹⁵. If no motor threshold is detected at 100% device stimulation intensity due to SCI (and interrupted circuits), the 100% stimulation intensity or the maximum tolerable intensity will be used. MEP responses will be measured during rest and during an active contraction (Motor Tasks, see below) before and after BoMI training, as well as with and without SCS. To estimate changes in MEPs, response amplitudes under different conditions will be normalized to the baseline (before training, resting) response.

Motor tasks: Immediately before after the BoMI session, participants will wear a VR headset (Oculus Quest 2, Facebook, CA) to block their view. The IMUs on the legs will measure and digitize their leg joint angles. A real-time virtual representation of one of their joint angles will be presented through the VR. Participants will be asked to perform two tasks requiring different types of motor control. In the range-of-motion task, participants will be instructed to flex or extend their legs to surpass a virtual target of a specified amplitude. In the precision-control task, participants will have to move their joint and hold the position within a target range of a specified amplitude for 1 second. We will examine motor-evoked potentials elicited by TMS (*Aim 1*) and the StartReact response (*Aim 2*) as individuals perform the task under two conditions: with SCS and without SCS using the knee and ankle joints. As an alternative to the VR headset, a wall projector will be used to perform the motor tasks.

BoMI Training: Participants will perform visuo-spatial motor tasks over a 45min session with SCS. The tasks will consist of different types of game-like activities like center-out reaching, pong, solitaire, Tetris, and other flash games.

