Expected outcomes, potential problems, and alternative strategies: Based on previous studies by other groups, it is our expectation that MEP responses will be enhanced for the precision-control task in distal muscles (tibialis anterior), which are thought to require a high involvement from the corticospinal tract. *We hypothesize that SCS will further enhance the MEP response for these movements, but not for range-of-motion movements, or movements with proximal muscles (rectus femoris).*

The main challenge in this study will be the recruitment of a sufficiently large group of volunteers with spinal cord injuries in the C4-T9 level. If this will not be feasible, we will extend the study to individuals with lesions at the C2-C3 level that have complete or partial paralysis in the legs. Furthermore, we can seek to further extend the study to other hospitals in the St. Louis region like the Barnes Jewish Hospital, the Rehabilitation Institute of St. Louis, SSM Rehabilitation Hospital, and the VA Medical Center Spinal Cord Injury Program. Another potential difficulty may arise because of the high expected attrition with severely disabled volunteers. As a consequence, some evaluations might be interrupted. To preserve uniformity of statistical power across the study, we will retain the results of participants with an incomplete number of sessions in separate data sets. The analysis of incomplete data sets will take explicitly into account the causes for abandoning the study (e.g. dissatisfaction with the methodology, change in medical condition, etc).

Our approach will have –by design an objective—a degree of customization based on each individual’s specific mobility and potential for movement restoration with SCS. Therefore, there might be a small initial difference in performance. However, our previous studies have demonstrated an improvement in performance with training independent of differences in the BoMI map between subjects^{22,62,66,67}.

One possibility is that 45 minutes of BoMI training is not sufficient to observe changes in corticospinal and reticulospinal tract excitability within a single session. If this is the case, we will increase the duration of BoMI training to 2 hours. Twenty minutes to 2 hours of SCS and motor training have been shown to be sufficient to observe changes in motor function^{61,68,69} as well as spinal¹⁵, cortical²⁴, and subcortical¹¹ excitability in human subjects.

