Average MEP and StartReact responses (of 20 responses) will be used to quantify changes in corticospinal and reticulospinal tract excitability¹⁵. A paired sample t-test of response amplitude and latency (time from stimulation to muscle response) will be used to test the hypothesis that BoMI training with SCS results in enhanced corticospinal tract excitability during precision-control movements and reticulospinal tract excitability during range-of-motion movements. In addition, a Student's *t*-test with a Holm-Sidak adjustment for multiple comparisons will be performed to compare the difference between changes in corticospinal excitability induced by the type of motor task (precision control vs. range-of-motion), joint (ankle vs. hip), and group (control vs. SCI).

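### Section 8 names one Student's t-test for task, joint and group without giving its form, although task and joint are within-subject and only group is between-subject

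*Combined protocol and SAP*

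**What the plan says.** Section 8 contains two test sentences. The first names "A paired sample t-test of response amplitude and latency" for the effect of BoMI training with SCS. The second adds a Student's t-test "with a Holm-Sidak adjustment for multiple comparisons will be performed to compare the difference between changes in corticospinal excitability" according to "the type of motor task (precision control vs. range-of-motion), joint (ankle vs. hip), and group (control vs. SCI". It does not say whether this second test is paired or how variances are handled, and no other section does.

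The Aim 1 part of section 7 describes the data. In its opening text, "participants will perform two motor tasks before and after training requiring different degrees of dexterity", and they do so "using two types of movements: hip vs. ankle flexion". Under Motor tasks, "Participants will be asked to perform two tasks requiring different types of motor control", examined "under two conditions: with SCS and without SCS using the knee and ankle joints". The second joint is therefore the hip in the Aim 1 introduction and in section 8, but the knee under Motor tasks.

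The Aim 1 hypothesis is one of selectivity: SCS should raise the MEP response for precision control in the distal muscle, "but not for range-of-motion movements, or movements with proximal muscles (rectus femoris").

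**The concern.** The three contrasts cannot share one form. Task and joint compare two values from the same person; group compares different people. Because the preceding sentence says paired and this one does not, and because the same named test must also serve control v SCI, an analyst would naturally run all three as unpaired tests with pooled variance.

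This matters for Aim 1, because it is the only test in section 8 that compares tasks or joints directly. A significant training effect in one condition and a non-significant one in another would not establish selectivity.

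Other parts of the contrasts are also open:
- whether a change means before/after training or with/without SCS (the TMS paragraph measures both);
- whether task is compared at one joint or averaged over both;
- whether task and joint are tested in each group or across groups;
- which task-joint value enters the group test.

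Two analysts could both follow section 8 and report different results.

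**Working it through.** The plan attaches no figure to this test. Section 8.4 gives no effect size, SD, alpha or power, so there is nothing to reproduce.

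**Inputs from the documents.** 12 SCI participants (section 8.4), and about 16 unimpaired participants per type of protocol (section 7.2, Participants). Controls attend either one of five visits or all five, which makes six types (100/16 is about 6). The TMS visit could therefore have 16 controls, or 16 + 16 = 32 if single-visit and five-visit controls both count.

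**Assumptions.** Normal data, two-sided 0.05, a difference of 0.8 SD, within-person correlation r, and SCI/control SD ratio 0.5 to 2.

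**Step 1: task and joint.** The true variance of the mean difference is 2(1−r)σ²/n, but the unpaired test uses 2σ²/n. The true standard error is thus √(1−r) times the one used, or 0.71 times at r 0.5. The paired standardized effect is 0.8/√(2(1−r)), which is 0.8 at r 0.5. With n=12 the noncentrality is 0.8 × √12 = 2.77 on 11 df, giving 71% power. Simulated power, unpaired v paired:

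| Sample | r 0.3 | r 0.5 |
|---|---|---|
| 12 SCI alone | 46% v 57% | 46% v 71% |
| 16 controls alone | 61% v 72% | 63% v 85% |
| 28 combined | 88% v 93% | 91% v 98% |

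The joint contrast uses different muscles, so its r may be lower: at r 0.2 and n=12 the figures are 46% v 52%, and break-even is at r about 0.1. At r 0 pairing costs about 1 to 4 points (47% v 43% at n=12).

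**Step 2: direction of the error.** With no true difference and n=12, the unpaired test at nominal 5% rejects in about 2.2%, 0.9% and 0.2% of trials at r 0.3, 0.5 and 0.7. It is conservative.

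**Step 3: Holm-Sidak.** If the groups are combined there are three tests, and the first step is 1 − 0.95^(1/3) = 0.0170. At that level 28 participants with r 0.5 give 77% v 95%. If task and joint are tested in each group there are 2 + 2 + 1 = 5 tests, and the first step is 1 − 0.95^(1/5) = 0.0102.

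**Step 4: group.** Pooled variance leans towards the larger group. At SD ratio 2 and 12 v 16, the expected pooled variance is (11×4 + 15×1)/26 = 2.27. The squared standard error used is 2.27 × (1/12 + 1/16) = 0.331, against a true 4/12 + 1/16 = 0.396. At 12 v 32 the same sums give 0.205 against 0.365. Simulated type I error of Student's test:

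| SCI/control SD ratio | 12 v 16 | 12 v 32 |
|---|---|---|
| 0.5 | about 3.6% | 1% |
| 1 | 5% | 5% |
| 1.5 | 6.5% | 10% |
| 2 | 7.7% | 14% |

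Welch stays near 5% throughout. At equal SDs and 0.8 SD it costs about 0.5 point of power at 12 v 16 (51.9% v 52.5%) and about 2 points at 12 v 32.

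**Step 5: task at one joint or averaged.** Suppose only the precision-ankle response rises, with equal correlation among the four task-joint values. The standardized effect is 0.4/√(1−r) for task averaged over joints and 0.8/√(2(1−r)) at the ankle. At r 0.5 these are 0.57 and 0.80, or 43% v 71% power at n=12. If instead the task effect is 0.8 SD at both joints, the averaged test has 94.5% and the ankle-only test 71%.

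**The case against.** The strongest reply is that the plan is silent rather than wrong. Student's t-test can name the whole family, paired form included. Section 8 applies it to a difference between changes, and section 8.4 speaks separately of within-subject and group changes. All of the power loss depends on an analyst running plainly repeated data unpaired. This stands as far as it goes: a reader might infer that the plan prescribes an unpaired test, and the documents do not say so. But section 8.4 assigns no form to any contrast, so the gap remains.

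Three other stronger readings also fail:
- **46% v 71% as the general loss.** It applies only if the SCI group is tested alone, which section 8 does not state. With the groups combined the loss is about 7 points at r 0.5.
- **Averaging over joints halves the detectable effect.** It halves the mean difference but also reduces noise; at r 0.5 the standardized effect is 0.57/0.80, or about 71% of the ankle-only one.
- **The group test sets 12 against 100.** Section 7.2 expects only about 16 controls per type of protocol.

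It is also fair that the training effect has an explicitly paired test, that this comparison is additional, and that section 3.1 presents the study as preparation for a later trial. These limit the severity. They do not remove the case for a clarification, since an inconclusive answer on selectivity would weaken that preparation.

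**Conclusion.** The point holds as under-specification with a natural reading that is inefficient for two contrasts and fragile for the third. For task and joint the cost is power only, under positive within-person correlation: from about 7 points (28 combined) to about 25 points (12 SCI alone) at 0.8 SD, r 0.5 and two-sided 0.05. A reader might infer inflated false positives for these contrasts; the calculation shows the opposite.

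For group, an unpaired test is right, and only the equal-variance assumption is at issue. Student's test is correct at equal SDs, liberal if the smaller SCI group is more variable, and conservative if it is less variable. The departure grows with the imbalance in group sizes.

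Effect size, correlation and SD ratio are all assumptions. The sentence covers corticospinal changes, so the point concerns Aim 1. It should be settled before analysis, but it does not undermine the design.

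**What to change.** In section 8, replace the single Student's t-test with a named form for each contrast, on one defined change in MEP amplitude per participant, task and joint, saying whether that change is before/after training or with/without SCS.

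- **Task and joint:** paired t-tests. State whether they are run in each group or with groups combined.
- **Group:** Welch t-test of control v SCI on one named task-joint value or average per participant. State whether five-visit controls, single-visit controls or both enter.
- **Multiplicity:** Holm-Sidak over three tests if the groups are combined, five if task and joint are tested by group.
- **Task contrast:** fix in advance whether it is taken at the ankle or averaged over joints. Ankle-only suits the stated hypothesis but is weaker if the effect is the same at both joints.
- **Supportive:** report the task-by-joint difference of differences with a 95% CI.
- **Wording:** reconcile the proximal joint, which is the knee under Motor tasks but the hip in the Aim 1 introduction and section 8.

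No extra data are needed. The statistical price is the small power loss shown above for pairing at zero correlation and for Welch at equal SDs.

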8.4 Sample Size

We plan to include in this study a total of 100 unimpaired and 12 SCI human volunteers over the course of two years. We expect that only 90% of unimpaired and 70% of SCI subjects initially recruited will conclude the experiment. Therefore, we will need to recruit 110 unimpaired and 16 SCI volunteers in order to reach the recruitment targets.

The number of subjects has been powered from the results of previous studies using similar methods to investigate structural changes in the brain after BoMI practice^{22,73}. Although the power is adequate, it might be possible that we are unable to detect significant changes in motor capacity. If no within-subject significant changes are found in preliminary experiments, we can extend the duration of training within one session, or extend the protocol to several sessions. If no significant group changes are found, we can recruit six more SCI participants for the study (a 50% increase).

9. Management of Intercurrent Events

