Study Title: Neural Facilitation of Movements in People With SCI
NCT number: NCT05354206
IRB ID #: 202111151 (The Washington University in St. Louis IRB)
PI: [name]
Document Type: Protocol
Document Date: 11/10/2022

Neural facilitation of stimulation-assisted movements in people with spinal cord injury

Principal Investigator:

[name]
Assistant Professor of Biomedical Engineering and Neurosurgery
Department of Biomedical Engineering
Washington University McKelvey School of Engineering
email: [contact]

Collaborators:

[name]
Instructor of Psychiatry
Department of Psychiatry
Washington University School of Medicine
email: [contact]

Study team members:

[name]
[name]
[name], OTD, OTR/L, ATP
[name]
[name], FNAI
[name]
[name]
[name], OTR/L, ATP
[name], PT, DPT, NCS

Version: November 10, 2022

Synopsis

Study title	Neural facilitation of stimulation-assisted movements in people with spinal cord injury
Objective	To understand the contribution of individual neural tracts to movements facilitated by transcutaneous spinal cord stimulation using transcranial magnetic stimulation, loud auditory stimuli, wearable sensors, motion tracking, and electromyography.
Hypothesis	Previous studies supported a potential role of spinal cord stimulation on the excitability of corticospinal and reticulospinal tract. We aim to identify the specific contributions of cortico- and reticulospinal networks towards reinforcing different types of movements enabled by transcutaneous spinal cord stimulation in unimpaired volunteers and volunteers with spinal cord injury. The results from this study may serve as preliminary data for the development of targeted rehabilitation strategies that take advantage of residual connections to maximize recovery after spinal cord injury.
Study period	Planned enrollment duration: approximately 12 months Planned study duration: 1-2 hours per subject, 5 visits
Number of subjects	112 (100 unimpaired, and 12 volunteers with spinal cord injury)
Study design	This study will measure changes in corticospinal and reticulospinal excitability associated with spinal cord stimulation during different leg movements.

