3.1 Rationale for this study

This 1-year study will provide the necessary data to prepare a clinical trial investigating whether activity-dependent reorganization of cortico- and reticulospinal circuits are primary contributors towards the long-lasting improvements in function that have been observed in humans. Moreover, we will study whether different types of training used in rehabilitation can be used to enhance the excitability of these neural structures and evaluate their role in the learning of skilled motor tasks²²⁻²⁵. An understanding of how we can accelerate plasticity through residual cortical and reticulospinal connections may enable the development of rehabilitation strategies that take advantage of patient-specific residual functions to further augment recovery.

4. Study Objectives

The goal of this project is to generate evidence-based knowledge of changes in the short-term excitability of corticospinal and reticulospinal neural structures that may mediate immediate improvements in motor function enabled by SCS.

Aim 1. Determine which kinds of SCS-facilitated movements are mediated by the corticospinal tract. I will use TMS to test whether SCS can enhance motor evoked potential (MEP) response time and amplitude as individuals use their legs to perform motor control tasks with different levels of dexterity.

Aim 2. Determine which kinds of SCS-facilitated movements are mediated by the reticulospinal tract. Using the same protocol, I will test whether SCS can enhance StartReact response time and amplitude.

5. Selection of Subjects – Inclusion/Exclusion Criteria

We plan to include in this study a total of 100 unimpaired and 12 SCI human volunteers over the course of one year.

Data collection will be performed at Washington University in St. Louis Danforth and Medical campus. Subjects will be referred by Drs. [name], [name], [name], [name], and [name], who are co-investigators on this project.

Approximately equal numbers of men and women will be recruited from all ethnic and racial groups. The racial composition of the population in St. Louis is approximately 44% Caucasian, 46% Black or African American, 4% Asian, 4% Hispanic, 2% Other. This will be the expected composition of our volunteer pool, of which the minority portion exceeds the national norm.

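### At section 8.4's own completion rates, recruiting 110 unimpaired and 16 SCI volunteers gives about 99 and 11 completers, not the 100 and 12 it claims

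*Combined protocol and SAP*

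**What the plan says.** Section 8.4 opens with the target: "We plan to include in this study a total of 100 unimpaired and 12 SCI human volunteers over the course of two years". It then gives the expected completion: "We expect that only 90% of unimpaired and 70% of SCI subjects initially recruited will conclude the experiment". From these it concludes that "we will need to recruit 110 unimpaired and 16 SCI volunteers in order to reach the recruitment targets".

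Elsewhere 100 and 12 appear without a distinction between people recruited and people completing. The synopsis lists 112 subjects (100 plus 12). Section 7.2 (Initial evaluation) repeats 100 and 12 as the participants. Section 5 gives "a total of 100 unimpaired and 12 SCI human volunteers over the course of one year", which also differs from section 8.4 on the length of the period.

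On participants who do not finish, the Expected outcomes text of section 7.1 (Aim 1) gives its reason as "To preserve uniformity of statistical power across the study" and then sets this rule: "we will retain the results of participants with an incomplete number of sessions in separate data sets". It adds: "The analysis of incomplete data sets will take explicitly into account the causes for abandoning the study". The procedure schedule places the TMS measurements for Aim 1 at Visit 4 and the StartReact measurements for Aim 2 at Visit 5. Under section 7.2, SCI participants are due all five visits, while unimpaired participants may attend one visit or all five.

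**The concern.** Section 8.4 presents 110 and 16 as what the completion rates require. If the rates are right, those numbers are expected to fall short of the targets that they are meant to secure. The SCI group is where this counts: it is small, its expected dropout is 30%, and one participant is about 8% of 12 (1/12).

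The secondary concern is also about how many SCI participants enter each aim's test. Read literally, the rule on incomplete sessions would set aside for Aim 1 an SCI participant who has complete Visit 4 data but misses Visit 5. That could cost usable paired data in the smallest group. It could also bias the comparison if leaving is related to response or tolerance.

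**Working it through.** **Inputs, all from section 8.4.** Targets 100 and 12; completion 90% and 70% (dropout 10% and 30%); stated recruitment 110 and 16.

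**Reproducing the stated figures.** Target × (1 + dropout):
- Unimpaired: 100 × 1.10 = 110.
- SCI: 12 × 1.30 = 15.6, rounded up to 16.

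Both match.

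**Expected completers from the stated figures.** Recruited × completion rate:
- Unimpaired: 110 × 0.90 = 99.0, which is 1.0 short of 100.
- SCI: 16 × 0.70 = 11.2, which is 0.8 short of 12.

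**Recruitment that the rates require.** Target / (1 − dropout):
- Unimpaired: 100 / 0.90 = 111.1, so 112, giving 112 × 0.90 = 100.8.
- SCI: 12 / 0.70 = 17.1, so 18, giving 18 × 0.70 = 12.6. Seventeen would give 11.9.

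Ordinary rounding of the correct formula gives 111 and 17, so rounding does not explain 110 and 16. Those figures reach the targets on average only if completion is 100/110 = 90.9% and 12/16 = 75%.

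**Chance of at least 12 SCI completers.** Binomial, assuming that participants complete independently. The 65% and 75% columns are a range assumed here around the plan's 70%.

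| SCI recruits | 65% complete | 70% complete | 75% complete |
|---|---|---|---|
| 16 | 29% | 45% | 63% |
| 17 | 42% | 60% | 77% |
| 18 | 55% | 72% | 86% |

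**Totals.** 110 + 16 = 126 recruits in section 8.4, against 112 subjects in the synopsis. With 112 and 18 the total would be 130.

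**The rule on incomplete sessions.** Three texts have to be read together. The schedule gives Aim 1 and Aim 2 different visits. Section 8 tests the effect of training with a paired t-test, and section 7.1 (Aim 1) takes the TMS responses before and after training, so Aim 1 needs no Visit 5 data. The rule refers to the number of sessions, is justified by power across the whole study, and names no exception by aim. Section 7.2 (Aim 2) and section 8 add none. The possible loss depends on when people leave, which the documents do not say. If losses are permanent and sequential, 16 − 11.2 = 4.8 SCI participants are lost in all. The number with Visit 4 data set aside for Aim 1 then lies between 0 (all leave before Visit 4) and 4.8 (all leave after it).

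**The case against.** **The shortfall is trivial.** This largely stands. It is about one person per group, and 12 is not a computed threshold: section 8.4 gives no significance level, power, effect size or standard deviation. A reader might infer that the trial is underpowered because of this slip, but the documents do not support that. For illustration, assume a two-sided 5% paired t-test with 80% power. The detectable standardised effect is then 0.89 with 12 participants and 0.94 with 11. At the effect that gives 80% power with 12, power with 11 is 76%. The chance of at least 12 completers measures how well the plan meets its own target, not whether it succeeds.

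**100 and 12 may be enrolment numbers.** The term recruitment targets and the synopsis total suggest this. But section 8.4 derives 110 and 16 from expected non-completion, which makes sense only if 100 and 12 are completers. If the sponsor means otherwise, the sentence still needs correcting.

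**The unimpaired total bears on no test.** This stands. Unimpaired participants may attend a single visit, with about 16 expected per type of protocol, and section 8 describes no analysis that needs 100 of them to finish. The unimpaired figure is an arithmetic correction only.

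**Six more SCI participants can be added.** Section 8.4 does allow this, but the trigger is a lack of significant group changes, not attrition.

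**The rule on incomplete sessions does not exclude anyone.** This stands in part. A reader might infer that participants with incomplete sessions are dropped from the main Aim 1 test. The text does not say so: it names no main data set, keeps the data, and promises an analysis that considers why people left. What remains is that incomplete is undefined and the analysis set for each aim is unstated.

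**Conclusion.** The sample-size sentence is wrong as written, and this part is held with high confidence. At the plan's own rates, 110 and 16 recruits give 99.0 and 11.2 expected completers; 112 and 18 are needed for 100 and 12. This rests only on reading 100 and 12 as completers, which the reasoning in section 8.4 requires. The effect is minor and falls mainly on the SCI group, where at 70% independent completion the plan is slightly more likely to miss 12 than to reach it (45% with 16 recruits). It is a correction to make, not a failure of the sample size.

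The point on incomplete sessions is secondary and held with lower confidence, because it is an inference from wording that does not state exclusion. It is a request for a definition.

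**What to change.** **Section 8.4.** Keep 110 and 16, and replace the claim that they reach the targets with a statement that about 99 unimpaired and 11 SCI participants are expected to complete. The alternative is to state 112 and 18 for 100 and 12 completers. That adds two recruits per group and is an enrolment decision for the sponsor and the IRB, not only a matter of wording.

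**Synopsis, section 5 and section 7.2 (Initial evaluation).** Give recruited and expected completing numbers separately, so that the synopsis's 112 and the 126 recruits of section 8.4 can be reconciled. If 112 is the approved enrolment total, stating 126 also needs the sponsor and the IRB. Reconcile the one-year period in section 5 with the two-year period in section 8.4.

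**Section 7.1 (Aim 1), rule on incomplete sessions.** Define incomplete against each participant's planned visits, since one visit is a full protocol for some unimpaired participants. Let each aim's main analysis include SCI participants who attended the preparatory visits and have that aim's paired measurements (Visit 4 for Aim 1, Visit 5 for Aim 2). Requiring the preparatory visits avoids pooling people with and without the Visit 3 familiarization. Report an analysis limited to SCI participants who completed all visits as a sensitivity analysis. This does not recover people who leave before the relevant visit, so any bias from their leaving remains.

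**Cost.** Keeping 110 and 16 needs changes of wording in these sections and one sensitivity analysis, and slightly lowers the stated completer numbers.
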